- To assess whether a Multicomponent Discharge Transition Intervention reduces the risk of early readmission compared to a control group following standard treatment.

- Secondary**

- To check whether the risk of early readmission is reduced with respect to the previous year in the experimental group and in the control group.

- To check whether early readmission rates are reduced in the experimental group compared with the control group and with respect to readmission rates in the previous year.

- Identify risk factors that are associated with early readmissions.

- To test whether a scale for estimating the risk of early readmission has adequate psychometric characteristics for such estimation.

- To test whether a Post-Discharge Recovery Support Psychotherapy Group improves outcome on measures of recovery, functioning, subjective well-being, social support, and satisfaction with mental health treatment in patients at high risk of early readmission.

- To test whether the Transition to Discharge intervention also reduces the risk of frequent readmission (revolving door).

- **Design**

The present study is a quasi-experimental cluster clinical trial aimed at assessing the efficacy of a multicomponent discharge transition program for the reduction of early readmissions in a MHHU. The development of this study consists of two distinct parts or elements:

To carry out the main objective, a quasi-experimental design with a control group will be used, and within the intervention, an early readmission risk assessment scale will be created to categorize patients into different risk levels.

In addition, a study will be conducted to assess the predictive value and validity of the early readmission risk rating scale and to study the risk factors for early readmission.

- **Setting**

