The present study will be carried out in the MHHU of the Regional University Hospital (RUH) of Malaga, a public hospital of the Andalusian Health Service. In addition to the Mental Health Clinical Management Unit of the HRU of Málaga, this MHHU is a reference for two other regional hospitals in the province of Málaga: The Málaga East Axarquía Hospital and North Málaga Health Management Area. The Mental Health Clinical Management Unit of the RUH of Malaga, according to figures from the 2022 database of users, serves a reference population of 336,968 people, while 150,823 people depend on the Mental Health Clinical Management La Axarquía and 109,958 depend on the Mental Health Clinical Management North of Málaga, resulting in a reference population of 597,749 people for hospitalization resources.

The MHHU has 40 beds in double rooms and is divided into two functional units. The access routes to hospitalization in this unit are admission from the Emergency Services, after evaluation by a psychiatrist, and programmed admission from another unit. The average occupancy rate is two thirds (28 beds) of the total capacity and the average stay in the year 2022 was 13.7 days, with a total number of admissions of 838. The data collected at the RUH of Malaga indicate an early readmission rate of 15.08% in the year 2022, using a time reference of 30 days until readmission.

The Spanish public health system is functionally organized into levels, with Primary Care comprising the first level and Ambulatory Specialized Care and hospital Emergency Services comprising the second level of care. The third level of care consists of hospital units with a high degree of specialization. The proposed intervention will primarily take place in the hospitalization unit (third level), as well as in the community-based outpatient care facilities

affiliated with said hospital, including the North Guadalmedina and Central Malaga Community Mental Health Units (second level).

- **Intervention and control group**

Intervention group

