The intervention program is based on the Discharge Transition Model for the prevention of hospital readmission in Mental Health. For its development, a multidisciplinary readmission commission was established, comprised of professionals from various categories and from different Mental Health facilities. The aim was to address this issue in detail and actively participate in the review of available evidence and decision-making regarding the development and implementation of the current program.

This is a multicomponent program that initially involves the development of a scale to assess the risk of readmission for each patient, followed by its systematic application. This allows for stratification of patients according to their risk of early readmission and adaptation of the intervention to the needs of each risk level. The intervention includes elements aimed at promoting continuity of care after discharge, transitioning back to the community setting, as well as elements aimed at enhancing personal and emotional resources through psychotherapeutic approaches. The following describes the different components of this intervention program.

Construction of the Early Readmission Risk Scale

For the preliminary analysis of risk factors associated with readmission, a retrospective observation will be conducted. This will involve analyzing all episodes from the previous calendar year stored in the database of the MHHU of the RUH of Malaga, provided that the records are complete. "Cases" will be selected from episodes that resulted in readmission within 30 days post-discharge, while an equivalent number of "controls" will be randomly selected through simple random sampling. Following this analysis, a measurement instrument will be developed to determine the risk of early readmission for all patients admitted to the MHHU.

A literature search was conducted to identify variables that have been associated with readmission and early readmission in other populations. The following variables were selected

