for analysis in the reference population: Sociodemographic factors (sex, age, marital status, legal incapacity, employment status, criminal history, and social functioning), psychiatric history (previous admissions, emergency service visits in the twelve months prior to admission, history of suicide attempts, attendance at community nursing follow-ups in the six months prior to admission, and somatic comorbidity), reasons for admission (presence of hetero- or auto-aggression or deficits in self-care), clinical characteristics (primary diagnosis, substance use, non-adherence to follow-up in the previous 12 months, and non-adherence to treatment up to one month before admission), admission characteristics (urgent or scheduled access route and length of stay), and discharge measures (coordination with referring physician in the CMHU and prescription of depot medication).

During admission to the hospitalization unit, all users must have the aforementioned Early Readmission Risk Scale of the MHHU of the RUH of Malaga administered. This will allow for the classification of patients according to their risk level, establishing defined cutoff points, resulting in three categories: Patients at low risk, medium risk, and high risk. This scale will be completed by the referring physician during the initial assessment interview upon admission to implement the proposed measures for each risk level. Additionally, the referring physician will establish contact with the case management figure responsible for the program for the referral of cases with a score indicative of a high risk of early readmission or patients with early readmission within 30 days post-discharge.

Intervention measures based on the risk of early readmission

For patients classified in the low-risk group, general measures would be applied. For patients in the medium-risk group, reinforced measures would be implemented. Lastly, for patients considered to be in the high-risk group, intensive case management measures would be applied, and if they meet the inclusion criteria, they would be included in the Post-Discharge Group Psychotherapeutic Intervention.

1. General measures

The following measures would be applied to patients with a low risk of readmission:

-Ensure coordination between physicians during admission and a follow-up appointment within 7 days.

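### The risk scale is derived in a 1:1 case-control sample with no stated correction to the ward's 15.08% readmission rate, so absolute risks, predictive values and tier sizes taken from that sample would be wrong; ranking is unaffected

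*Combined protocol and SAP*

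**What the plan says.** Under Methods, Construction of the Early Readmission Risk Scale, the source is described as "analyzing all episodes from the previous calendar year stored in the database of the MHHU of the RUH of Malaga, provided that the records are"; incomplete records are thus left out. The case group is "selected from episodes that resulted in readmission within 30 days post-discharge". For the comparison group the wording is "while an equivalent number of 'controls' will be randomly selected through simple random sampling". The text does not say whether controls come from non-readmitted episodes only or from all episodes. The resulting instrument is meant to determine risk for every patient admitted to the unit.

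Under Setting, the unit's data "indicate an early readmission rate of 15.08% in the year 2022, using a time reference of 30 days until readmission", and "the average stay in the year 2022 was 13.7 days, with a total number of admissions of 838".

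A secondary aim reads "To test whether a scale for estimating the risk of early readmission has adequate psychometric characteristics for such estimation", and the Design section promises a study of the scale's predictive value and validity, without giving a method. On use at admission: "This will allow for the classification of patients according to their risk level, establishing defined cutoff points, resulting in three categories" (low, medium and high). No probability is attached to any category.

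Data analysis specifies univariate and then forward stepwise logistic regression, with sensitivity and specificity examined on an ROC curve. Nothing there or elsewhere mentions sampling weights, an intercept correction, calibration, or predictive values at the ward rate. Construction is said to follow a cited procedure, but bibliography item 23 is titled as a study of cognitive behavioral therapy for anxiety disorders. The documents therefore do not show whether that procedure resets the baseline risk.

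**The concern.** Sampling on the outcome fixes the readmitted proportion by design. A logistic model fitted to such a sample keeps its slopes, but its intercept belongs to the sample and not to the ward. Any quantity that depends on prevalence inherits the error: predicted risk, positive and negative predictive value, and the share of patients above a cut-off. The plan says it wants to estimate risk and assess predictive value, and these are the quantities affected.

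Two things are at stake. First, a risk or predictive value attached to a score and reported from the derivation sample would overstate readmission considerably, and tier sizes planned from it would not match the ward's workload. Second, most non-readmitted episodes are left out although the plan describes the whole year's episodes as its source. That costs precision in choosing and weighting items from more than 20 candidate variables by stepwise selection.

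**Working it through.** **Inputs from the documents:** 838 admissions and a 30-day readmission rate of 0.1508 in 2022 (Setting); one control per case (Construction of the scale).

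**Assumptions:** the derivation year and its complete records resemble 2022; sensitivity/specificity pairs of 0.60/0.80, 0.70/0.70 and 0.80/0.60, since the plan gives none.

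**1. Counts.** 838 × 0.1508 = 126.4. The stated rate cannot be reproduced exactly: 126/838 = 15.04% and 127/838 = 15.16%. Its numerator and denominator are not given (125/829, for example, would fit), so it cannot be called wrong. I use 126 cases and 838 − 126 = 712 non-cases, as approximations.

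**2. Make-up of the sample.** Controls from non-readmitted episodes: 126/252 = 50% readmitted. Controls from all episodes: (126 + 126 × 0.1508)/252 = 57.5%. Steps 3 to 6 take the first case.

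**3. Intercept.** All cases and 126/712 = 17.7% of non-cases are used. The intercept rises by ln(0.8492/0.1508) = ln(5.63) = 1.728, so odds are multiplied by 5.63.

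| True ward risk | Risk read from the 1:1 model |
|---|---|
| 5% | 23% |
| 15% | 50% |
| 30% | 71% |

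In reverse, an uncorrected 30% means 7.1%, and an uncorrected 70% means 29.3%.

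**4. Check by simulation** (three assumed predictors with log odds ratios 0.8, 0.6 and 0.5; prevalence 15.08%). Slopes were 0.81/0.60/0.50 with all episodes and 0.81/0.59/0.50 at 1:1; AUC was 0.686 and 0.685. The intercept shift was 1.727. Mean predicted risk over all episodes was 46.3% uncorrected and 15.1% after subtracting 1.728, against 15.1% observed.

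**5. Predictive values and share flagged.** With prevalence π, PPV = π·Se/[π·Se + (1 − π)(1 − Sp)], NPV = (1 − π)·Sp/[(1 − π)·Sp + π(1 − Se)], and the share flagged is π·Se + (1 − π)(1 − Sp).

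| Se/Sp (assumed) | PPV, sample | PPV, ward | NPV, sample | NPV, ward | Flagged, sample | Flagged, ward |
|---|---|---|---|---|---|---|
| 0.60/0.80 | 75% | 35% | 67% | 92% | 40% | 26% |
| 0.70/0.70 | 70% | 29% | 70% | 93% | 50% | 36% |
| 0.80/0.60 | 67% | 26% | 75% | 94% | 60% | 46% |

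For 0.70/0.70 on the ward: 0.1508 × 0.7 = 0.1056, 0.8492 × 0.3 = 0.2548, flagged = 0.3603, PPV = 0.1056/0.3603 = 0.293.

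**6. Precision.** Near the null, the variance of a log odds ratio is proportional to 1/cases + 1/controls. The standard error ratio is √[(1/126 + 1/126)/(1/126 + 1/712)] = 1.30. In 500 simulated years of 838 episodes, slope standard deviations were 0.256/0.285/0.135 at 1:1 and 0.201/0.208/0.097 with all episodes, which is 27% to 39% larger.

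**The case against.** Case-control derivation is a legitimate and efficient design. The only performance check named is an ROC curve, and sensitivity, specificity and AUC are not biased by sampling on the outcome. The scale is used through cut-offs that form three ordered groups. Some candidate items, such as criminal history, social functioning and past non-adherence, may need chart abstraction, so sampling may have a practical reason. The plan calls this step a preliminary analysis and promises a later study of predictive value, where ward-level figures could be reported. All of this stands, except that the later study has no stated method and so does not close the gap.

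A reader might infer two stronger conclusions:

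- **That the scale cannot estimate readmission risk at all.** The documents do not support this. Only the intercept is displaced, and a known offset restores it.
- **That the low, medium and high tiers are invalid.** This would follow only if cut-offs were set on predicted risk, on predictive value or on the share flagged in the derivation sample. No section says so, and the method named is the ROC curve. Tiers set that way keep their order and meaning; only their sizes and predictive values need restating for the ward.

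It is also fair that the 50% and the 1.73 are inferred. They require non-readmitted controls and a case mix among complete records like that of the ward.

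**Conclusion.** The point holds in a limited form. As written, the plan does not support absolute risks, predictive values or tier sizes taken from the derivation sample, although estimating risk and predictive value is among its aims. Odds would be inflated about 5.6-fold. Over the assumed sensitivity and specificity pairs, PPV would read 67% to 75% in the sample against 26% to 35% on the ward. Log odds ratios would have standard errors about 30% larger near the null than the year's episodes allow.

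These sizes rest on non-readmitted controls, about 126 cases and 712 non-cases, and assumed accuracy figures. Drawing controls from all episodes would change the numbers, but at about 57.5% readmitted the sample would still be far from 15.08%.

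The primary comparison is not affected: it models observed readmission between groups and adjusts for the scale's variables, not for a calibrated risk. This is an inexpensive improvement to the scale, not a threat to the main result.

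**What to change.** In Construction of the Early Readmission Risk Scale, replace the 1:1 sampling with a fit to all complete episodes of the previous year. No correction is then needed, and the lost precision is recovered.

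If sampling is kept because items need chart abstraction:

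- State that controls are drawn from non-readmitted episodes, and record the actual sampling fraction.
- Weight controls by the inverse of that fraction, or offset the intercept by its logarithm. The offset is about −1.73 if complete records match the 15.08% rate; it should be computed from the actual counts, not fixed in advance.

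Under either option, add to Data analysis a calibration check, and report PPV, NPV and tier sizes at the ward rate, over a range of sensitivity and specificity until these are observed. Calibration should be judged first in the pre-programme year, because the programme itself may change readmission risk in the year that follows.

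Cost: the all-episodes option may require abstracting up to about 712 − 126 = 586 further episodes if some items are not already coded. The weighting or offset costs almost nothing.

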In the analysis for the creation of the early rehospitalization risk scale, a univariate logistic regression analysis will be used. For the final selection of factors, a forward stepwise multivariate analysis will be performed, introducing variables with greater statistical significance. Finally, a scale will be developed to measure the risk of early rehospitalization in each admission episode, whose sensitivity and specificity will be tested beforehand using a receiver operating characteristic (ROC) curve. The construction of the scale will follow the procedure outlined in detail in Sullivan et al. (23).

To evaluate the differences between the intervention group and the control groups, a univariate and multivariate mixed logistic regression analysis will be conducted, introducing potential confounding variables (unit occupancy, age, sex, and the variables used in the scale for estimating the risk of early rehospitalization). To assess potential differences in Core Om, Duke-unk-11, PSP, and QPR among patients participating in the Post-Discharge Recovery Support Psychotherapy Program, the paired Student's t-test for repeated measures or the non-parametric Wilcoxon signed-rank test for a single sample will be used.

DISCUSSION

The present research study aims to analyze the risk factors for early rehospitalization of patients discharged from a short-term psychiatric hospitalization unit. Based on this information, the goal is to stratify the risk and direct more intensive therapeutic measures to those individuals with a higher likelihood of rehospitalization to reduce early rehospitalization rates.

Thus, determining the risk of psychiatric rehospitalization for individual patients is a critical step in efforts to address the potentially avoidable high rate of this negative outcome, as highlighted in the READMIT study (4). This study conducted in Canada succeeded in providing a framework to identify patients at high risk of rehospitalization through the development of a prognostic index with moderate discriminative capacity.

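### No rule keeps variables unknown at the admission interview out of the risk scale; if coordination with the CMHU physician is selected, the multivariate outcome model would adjust for what is probably a programme measure

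*Combined protocol and SAP*

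**What the plan says.** All references are to the combined protocol and SAP.

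- **Scoring time** (Construction of the Early Readmission Risk Scale): "This scale will be completed by the referring physician during the initial assessment interview upon admission". The score sets the patient's tier and hence the measures to be applied.
- **Candidates** (same section): one group on the list is "admission characteristics (urgent or scheduled access route and length of stay". The list then closes with a further group: "and discharge measures (coordination with referring physician in the CMHU and prescription of depot medication". The plan itself classes the two items of this closing group as discharge measures.
- **From candidates to scale** (same section): "Following this analysis, a measurement instrument will be developed to determine the risk of early readmission".
- **Selection rule** (Data analysis): after univariate regressions, "a forward stepwise multivariate analysis will be performed, introducing variables with greater statistical significance". Nothing is said about when an item becomes known.
- **Outcome models** (Data analysis): "a univariate and multivariate mixed logistic regression analysis will be conducted, introducing potential confounding variables". Besides sex, age and how full the unit is, the covariate list ends with this item: "and the variables used in the scale for estimating the risk of early rehospitalization". Neither the univariate nor the multivariate model is named as primary.
- **Programme content** (General measures): the first measure is "Ensure coordination between physicians during admission and a follow-up appointment within 7 days". The reinforced and intensive levels are each stated to add to the levels below, so this measure applies in every tier. Control participants receive usual treatment.

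**The concern.** Two things can go wrong if the plan is followed as written and a late variable is selected.

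1. **Score.** Points, ROC curve and cut-offs would be derived on completed episodes, where the late item is known. At the admission interview it is not. The physician must leave it out or guess it, and the cut-offs no longer fit. Patients could be placed in too low or too high a tier.
2. **Estimate.** A scale variable automatically becomes a covariate. If coordination is a programme measure, adjusting for it conditions on something the programme changes, and the part of the effect that works through coordination drops out of the multivariate estimate.

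The second matters because allocation is not randomised, as the Discussion acknowledges. The univariate model escapes the problem but does nothing about possible confounding. The multivariate model is where confounding is handled, and it is the one exposed.

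**Working it through.** The plan gives no effect size, coverage figure or selection threshold, so there is no stated figure to reproduce. The documents supply 838 admissions and a 15.08% early readmission rate in 2022 (Setting). Every other input below is an assumption.

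**Step 1: count the candidates.** Sociodemographic 7 + history 5 + reasons for admission 1 to 3 (depending on how they are split) + clinical 4 + admission 2 + discharge 2 = 21 to 23. Three are not known at the interview, leaving 18 to 20.

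**Step 2: could a late item be selected?** Cases: 838 × 0.1508 ≈ 126, with an equal number of controls (fewer if records are incomplete). Assume a two-sided 5% univariate threshold. With prevalence q in controls and p in cases, SE of the log OR = √[(1/126)(1/q + 1/(1−q) + 1/p + 1/(1−p))], and power ≈ Φ(|ln OR|/SE − 1.96). Example, OR 0.5 and q = 50%: p = 33.3%, SE = √(8.5/126) = 0.260, 0.693/0.260 − 1.96 = 0.71, power 76%.

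| OR | q = 30% | q = 50% | q = 70% |
|---|---|---|---|
| 0.8 | 12% | 14% | 13% |
| 0.5 | 63% | 76% | 75% |

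Selection is plausible for a strong effect and unlikely for a weak one. The later stepwise stage could change these figures.

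**Step 3: effect on tiering.** Simulation of 2,000,000 episodes: readmission 15.08%, other items normal on the log-odds scale with SD 0.8, one binary late item with OR 2.0, cut-off flagging the top 20% on the full score.

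| Scoring at admission | Prevalence 25%: flagged / sens. / spec. | Prevalence 50%: flagged / sens. / spec. |
|---|---|---|
| Full score (item known) | 20% / 0.43 / 0.84 | 20% / 0.43 / 0.84 |
| Item scored absent | 13% / 0.30 / 0.90 | 9% / 0.22 / 0.94 |
| Item scored present | 40% / 0.65 / 0.64 | 31% / 0.56 / 0.73 |
| Item dropped, cut-off reset to 20% | 20% / 0.41 / 0.84 | 20% / 0.41 / 0.84 |

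Most of the harm is a cut-off that no longer fits. Dropping the item and resetting the cut-off costs about 0.02 in sensitivity (0.005 to 0.046 over SD 0.6 to 1.0, OR 1.5 to 2.5, prevalence 25% to 50%).

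**Step 4: effect on the estimate.** Set the risk without coordination so that the overall rate is 15.08% at usual coverage. Then apply the programme's coverage and a direct OR for the rest of the programme. Share removed = 1 − ln(direct OR)/ln(total OR).

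Worked case: coordination OR 0.6, coverage 50% to 95%, direct OR 0.8.
- Usual care: risk 18.31% without and 11.85% with coordination; the mean is 15.08%.
- Programme: 15.20% and 9.71%; 0.05 × 15.20 + 0.95 × 9.71 = 9.99%.
- Total OR = (0.0999/0.9001)/(0.1508/0.8492) = 0.625, against 0.80 after adjustment.
- Share removed = 1 − 0.223/0.470 = 53%.

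| Coordination OR | Coverage | Removed, direct OR 0.8 | Removed, direct OR 0.6 |
|---|---|---|---|
| 0.5 | 30% to 95% | 68% (total OR 0.498) | 48% (0.374) |
| 0.8 | 70% to 90% | 17% (0.764) | 8% (0.573) |
| 0.5 | 85% to 95% | 27% (0.737) | 14% (0.553) |
| 0.8 | 85% to 95% | 10% (0.781) | 4% (0.586) |

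The share compares a marginal total OR with a conditional direct OR, so it shows direction and rough size only.

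**The case against.** **The candidate list has another legitimate use.** Identifying risk factors is a separate secondary aim, and late variables belong there. A physician also cannot complete an item that does not yet exist, so developers might drop it. This stands as far as it goes. But the text describes one route from candidates to scale, with no filter on it.

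**The harm is conditional.** The final items are not in the document, and Step 2 shows that a weak effect would seldom be selected. This stands. It limits the point to a missing rule.

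**The measure is not said to be the candidate.** The general measure speaks of physicians without naming the CMHU; the candidate names it. Treating them as the same is natural in a programme about continuity with community units, but it is an inference, and the second consequence depends on it.

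**The illustrations rest on chosen inputs.** This stands. The control areas are served by the same inpatient unit, so usual coverage could already be high, and the share removed would then be small. The single cut-off in Step 3 also simplifies a three-tier scale.

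**Removing coordination has a price.** Groups are defined by CMHU affiliation, so an earlier difference between areas in coordination would stay unadjusted. This stands and is counted under the fix.

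A reader might go further and infer any of the following. The documents support none of them.
- *The main estimate is biased.* The items are unknown, and a univariate model free of this problem is also planned.
- *The univariate estimate is confounded.* The Discussion says only that non-random allocation may introduce bias.
- *Mis-tiering biases the programme-versus-control contrast.* By itself it changes who receives which measures, not that comparison.
- *All three late variables are equally serious as covariates.* Depot medication is only to be considered, in the high-risk tier. No tier measure targets length of stay; only a general remark in the Introduction links such programmes to earlier discharge.

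**Conclusion.** The point holds as a gap in the rules. It is certain that three candidates are unknown when the scale is scored, that no text excludes them, and that any selected item becomes a covariate. Whether a late item will be selected is not known.

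If one is, the tested score is not the one that can be applied at admission. If it is coordination, and coordination is the programme measure, the multivariate estimate would tend towards no effect, provided coordination is protective. Under the assumed inputs the share of the log OR removed runs from about 4% to 68%. That range shows that the effect can be negligible or large; it does not estimate it. The change is worth making because it is cheap and is best made before items are selected.

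**What to change.** 1. **Construction of the Early Readmission Risk Scale:** state that only variables known at the admission interview may enter the scale, and derive points, ROC curve and cut-offs on that set (18 to 20 candidates). Keep length of stay, coordination and depot prescription for the separate risk-factor analysis.
2. **Data analysis:** limit the adjustment set to variables fixed before the programme can act, so that coordination in particular is not a covariate.
3. If a later scoring time is intended, the statement on scoring at admission and the tier measures that act during the stay must be reconciled.

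**Cost:** two sentences and no new data. Apparent discrimination may be slightly lower, about 0.02 in sensitivity under the illustrative model. Any earlier difference between areas in coordination would remain unadjusted at episode level; the planned comparison with the previous year in the same area partly addresses this.
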